6.6.2.5 Non-completers considered failure (NCF)

For binary endpoints, like a treat to target response of HbA1c < 7.0%, a method that missing values are replaced as “failures” will be considered. Missing data due to early discontinuation per the completer definition will be replaced as “failure” (i.e., HbA1c $\geq 7.0\%$) up to the

planned final visit to be reached by all patients. In addition, values obtained after rescue medication will also be handled as “failure”.

For binary endpoints that are derived from quantitative endpoints (e.g. HbA1c), missing values within a course of measurements on treatment will be replaced on the basis of the corresponding imputed value of the underlying quantitative endpoint (e.g. interpolation for HbA1c).

6.6.3 Safety and other variables

Missing safety data will not be replaced.

6.6.4 Missing dates and times

a) Missing AE dates

Missing or partial date information for AEs will be replaced according to general BI rules described in the BI guidance for “Handling of missing and incomplete AE dates” ([5](#)).

b) Missing drug administration dates

If the date of first drug administration is missing but the patient was randomised, the date of the first drug administration will be set to the date of randomisation.

If the date of first administration is partially missing with the month and year present, the day will be set to the date of randomisation if randomisation was in the same month. If randomisation was in the month prior to the first drug administration the missing day will be imputed as the first day of the month. A missing time of first drug administration will be imputed as 12:00 o'clock noon, missing administration times at on-treatment visits will be imputed by 08:00 o'clock in the morning.

If the date of trial medication stop is partially or completely missing, use the minimum of the following dates:

- End of treatment visit date, if available
- Date of death
- Trial completion (last contact date)
- Longest extrapolated treatment duration (assuming 1 tablet/day)
- (in case for partially missing date) Last day of the year/month given as partial date

In case of a partially missing date, if the imputed date is before the first day of the month/year given as the partial date, the first day of the month/year will be used. All other cases need to be assessed by the trial team on an individual patient basis, using the points above as guidance.

c) Missing dates for concomitant and other antidiabetic therapies

For incomplete date information, the midpoint of the possible interval will be used. If only the year is present, the day and month will be imputed as 01 July, if year and month is present the day will be imputed as 15. If the year is missing, the date will be considered missing.

If this leads to contradictions for the start or end date of a concomitant therapy (e.g. imputed end date before documented start date), a partial end date will be imputed as the end of the interval or a partial start date will be imputed as the start of the interval in the database to resolve this contradiction.

All other cases or conflicting cases resulting from these imputation rules need to be assessed by the trial team on an individual patient basis.

6.7 BASELINE, TIME WINDOWS AND CALCULATED VISITS

With regard to efficacy and safety endpoints, the term “baseline” refers to the last observed measurement prior to administration of any randomised trial medication. Measurements taken prior to the first intake of randomised trial medication will be considered pre-treatment values. Since the protocol specifies that all measurements are taken at Visit 3 before any intake of trial medication, all measurements at the first day of drug intake are assumed to qualify as baseline assessments.

Measurements taken after the first intake of randomised trial medication will be considered on-treatment values if they have been obtained up to end of the parameter specific follow-up period as defined in [Table 6.7:1](#) below and will be assigned to the randomised trial medication for efficacy and safety analyses.

Measurements taken after the end of the endpoint specific follow-up period and after the last intake of trial medication will be considered post-treatment values.

On-treatment efficacy, safety, health related and QoL measurements will be assigned to visits based on time windows around the planned visit dates. These time windows are defined based on the planned number of days after the date of first administration of trial medication (see [Table 6.7: 2](#)).

Table 6.7: 1 Endpoint specific assignment to active treatment

Endpoint	Last day of assignment to treatment phase
-----------------	--

		(days after trial medication stop date)
Efficacy		
HbA1c		7
Safety		
Adverse events		7
Safety laboratory measurements		3
Pulse rate		1
FPG		1
Chair stand test		7
Grip strength		7
Body composition		7
[REDACTED]		[REDACTED]

Reasons to base the time windows on the actual treatment start date rather than the randomisation date are:

- If first intake of trial medication shows a large delay by e.g. more than one week after the date of randomisation, a measurement taken four weeks after randomisation rather reflects the drug effect after three weeks than after four weeks and thus may underestimate the treatment effect at this visit.
- With large delays of the introduction of trial medication after the randomisation, the time window for the first on-treatment visit could include times the patient was not yet on trial medication.

The time window for the first visit after randomisation starts on the day after the first intake of trial medication. This maximises the number of measurements used in by visit analyses, but may lead to an underestimation of the treatment effect at the first visit for parameters that react slowly on treatment.

The midpoint between two on-treatment visits defines the end of a time window, with the midpoint being included in the time window of the preceding visit. The end of the time window of the last on-treatment visit (EOT) is endpoint dependent (cf. [Table 6.7: 1](#)).

Table 6.7: 2 Time windows for on-treatment efficacy measurement scheduled for each on-treatment visit

			Time Window (actual days on treatment)	
Visit number	Visit label	Planned days	Start	End ^A

3	Baseline	1	NA	1 ^B
4	Week 4	29	2	57
5	Week 12	85	58	127
6	Week 24	169	128	211
7	Week 36	253	212	309
8	Week 52/EOT	365	310	Trial medication stop date + X days

A. In case of premature discontinuation of the trial medication a Visit 8 has to be performed. If such a Visit 8 falls into the time window of a previous visit, measurements will be assigned to this previous visit and the visit value will be determined as described below. In this case the time window for the visit that includes Visit 8 will end X days after the trial medication stop date, including Day X. The definition of X is endpoint specific, cf. [Table 6.7: 1](#). No time window for optional visit is planned.

B. Only values taken prior to the start of treatment with randomised trial medication can be considered baseline values. Time windows will be used for assignment of measurements to scheduled visits.

Only one observation per time window will be selected for analysis at an on-treatment visit - the value will be selected which is closest to the protocol planned visit day. If there are two observations which have the same difference in days to the planned day or if there are two observations on the same day, the first value will be used.

Note: For LOCF imputation, the last observed on-treatment value will be carried forward within the applicable period, whether or not it was selected in the previous time window. For interpolation only selected values are to be used. For more details on LOCF refer to [Section 6.6](#).

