5. ASSESSMENTS

5.1 ASSESSMENT OF EFFICACY

5.1.1 HbA1c

HbA1c is considered appropriate to evaluate the efficacy as primary endpoint because HbA1c is an internationally accepted endpoint of stable glycaemic control.

Blood samples for the determination of HbA1c at the central laboratory will be taken at all the visits except Visit 2, the blood sample can be taken at any time during the visit. For the determination of HbA1c, 3 mL of blood will be collected. The samples will be analysed at a central laboratory having a National Glycohaemoglobin Standardisation Program (NGSP) Level I certificate. Further details about sample handling, shipment, and assay procedures can be found in the ISF (Lab manual).

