6.2.3 Follow-up period and trial completion

A Follow-up visit will be performed 7 days (+7 day window) after the last dose of trial medication. The assessments to be performed at the follow-up visit are indicated in the flowchart. The follow-up visit marks the completion of the study for the individual patient who completed the study on trial medication.

See section [3.3.4.1](#) for procedures to be followed in case a patient prematurely discontinues trial treatment.

For patients who early discontinued trial medication but followed up according to the visit schedule, Visit 9 (EOS) marks the completion of the study for the individual patient.

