6.6.2.2 Observed cases (OC) analysis

For all efficacy endpoints, it is planned to analyse only the available data that were observed while patients were on treatment, i.e., excluding the missing data. In other words, OC analysis will be performed and missing data in this analysis will not be replaced. Also, all values measured after rescue medication will be handled as missing (rescue medication as defined in [Section 6.6.1](#)).

The OC-technique represents the primary data selection tool that will be used for the primary analysis in this trial. Subsequent handling of missing data will be performed via a likelihood based method, and in the case of the primary analysis, will use the MMRM model.

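### SAP 6.7 lets an HbA1c sample taken at Visit 9, up to 7 days after the last dose, replace the Visit 8 sample as the Week 52 value

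*SAP*

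**What the plan says.** Five rules combine.

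- **Sampling.** Protocol 5.1.1: "Blood samples for the determination of HbA1c at the central laboratory will be taken at all the visits except Visit 2". Visit 9 (EOS) is therefore included.
- **Timing of Visit 9.** Protocol 6.2.3: "A Follow-up visit will be performed 7 days (+7 day window) after the last dose of trial medication". Protocol 3.1 and the footnotes to the safety laboratory tables instead place it one week after the EOT visit.
- **On-treatment status.** SAP 6.7: values after first intake "will be considered on-treatment values if they have been obtained up to end of the parameter specific follow-up period". Table 6.7: 1 sets this period for HbA1c at 7, in units of "days after trial medication stop date".
- **Week 52 window.** Table 6.7: 2 opens it on Day 310, with planned day 365, and closes it at "Trial medication stop date + X days", so at stop date + 7 for HbA1c. Visit 9 has no window of its own.
- **Selection.** When a window holds several values, "the value will be selected which is closest to the protocol planned visit day"; a tie goes to the first value.

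SAP 6.6.2.2 makes observed cases the data selection for the primary analysis and says that "it is planned to analyse only the available data that were observed while patients were on treatment". No visible text excludes an EOS sample from the Week 52 window or gives the EOT sample priority.

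**The concern.** A Visit 9 done on its nominal day falls exactly on the last eligible day of the Week 52 window. The choice between the two samples then depends on calendar distance to Day 365, not on which was taken at the end of treatment. A completer who attends Visit 8 a few days early can have the planned end-of-treatment value set aside for one drawn a week after the last dose.

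The primary endpoint is the change after 52 weeks of treatment. Only the empagliflozin arm stops an active drug, so any movement of HbA1c in that week is likely to shrink the difference. Which patients are affected is decided by scheduling alone.

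**Working it through.** **Plan's own figure.** Protocol 7.5 assumes a difference of 0.5, SD 0.85, two-sided 5% and 62 evaluable patients per group. The noncentrality is 0.5 / (0.85 x sqrt(2/62)) = 3.275, and the exact two-sample t-test then has 90.1% power. Allowing for 3% outside the FAS, 62 / 0.97 = 63.9, so 64 per group. The stated sample size reproduces.

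**Windows.** The midpoints of planned days 29, 85, 169, 253 and 365 are 57, 127, 211 and 309, as in Table 6.7: 2. The Week 52 window therefore opens on Day 310.

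**When Visit 9 is selected.** Let Visit 8 be k days before Day 365.

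- Last dose on the Visit 8 day, Visit 9 at last dose + 7: Visit 9 is selected if |7 - k| < k, so k >= 4, meaning Visit 8 on Day 361 or earlier. Example: Visit 8 on Day 360 is 5 days off and Visit 9 on Day 367 is 2 days off, so Visit 9 is used.
- Last dose the day before Visit 8, Visit 9 at last dose + 7 (Visit 8 + 6): |6 - k| < k. At k = 3 there is a tie, which goes to Visit 8, so the threshold is again k >= 4.
- Last dose the day before Visit 8, Visit 9 at EOT + 7 (last dose + 8): outside the window, never selected.
- Any Visit 9 that is 8 or more days after the last dose: never selected.

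**Share of completers affected.** The permitted window around Visit 8 is not shown, so it is assumed here. Visit 8 is taken as uniform over the window, with the last dose on that day. If Visit 9 is uniform over days 7 to 14, only one of the eight days is eligible, so the share is divided by 8.

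| Assumed Visit 8 window | Visit 9 always on day 7 | Visit 9 uniform over days 7 to 14 |
|---|---|---|
| +/-3 days | 0/7 = 0% | 0% |
| +/-5 days | 2/11 = 18% | 2.3% |
| +/-7 days | 4/15 = 27% | 3.3% |
| +/-14 days | 11/29 = 38% | 4.7% |

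**Effect on the difference and power.** The documents give no figure for the change in HbA1c over a week off drug. Assume that the effect decays from the last dose with a half-life h of 20, 30 or 45 days. The share of the effect lost is 1 - 0.5^(7/h) = 21.5%, 14.9% or 10.2%, or 0.11, 0.07 or 0.05 points out of 0.5. The expected difference is 0.5 x (1 - loss x share), with 62 per group and SD 0.85 as above.

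| +/-7 day Visit 8 window | h = 20 | h = 30 | h = 45 |
|---|---|---|---|
| Share 27%: difference | 0.471 | 0.480 | 0.486 |
| Share 27%: power | 86.5% | 87.7% | 88.5% |
| Share 3.3%: difference | 0.496 | 0.498 | 0.498 |
| Share 3.3%: power | 89.7% | 89.9% | 89.9% |

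If HbA1c does not move in that week, nothing is lost at any share.

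**The case against.** The strongest reply is that the SAP sets the 7-day allowance on purpose. Protocol 1.2 gives a residual effect period of 7 days, in which drug levels or effects are still likely to be present. A reader might infer that the affected patients contribute washout values. The documents do not support that: such a sample is on-treatment by the SAP's definition and lies at the edge of the residual effect period. What remains is that the allowance does not justify preferring this sample over an available end-of-treatment sample. The allowance also has a separate use, because Protocol 6.2.2 permits an EOT visit within 7 days of stopping.

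Three other stronger readings also fail.

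- **A large share affected.** The 27% needs every Visit 9 to fall on day 7. Protocol 6.2.3 allows days 7 to 14, and if EOS is counted from EOT with the last dose on the day before, no swaps occur.
- **Contamination by new antidiabetic therapy after Visit 8.** SAP 6.6.1 and 6.6.2.2 treat additional therapy used for 7 or more consecutive days as rescue and set later values to missing. Shorter use is not caught, and OC-IR keeps values after rescue by design. The SAP does not say that censoring precedes selection. If it came second, Week 52 could be missing although a Visit 8 value exists.
- **Displacement under LOCF in completers.** LOCF fills missing values, so a completer with a Week 52 value has nothing to fill. The issue is limited mainly to early stoppers whose EOS sample falls within 7 days of the last dose.

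Scheduling is blinded and the likely bias is towards no difference, so there is no case for inflated type I error.

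**Conclusion.** The selection rule has a real gap. It can discard an existing end-of-treatment HbA1c for one drawn about a week after the last dose, for completers with Visit 8 on Day 361 or earlier and Visit 9 no later than day 7. That follows from the plan's own rules and needs no assumption.

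The size does rest on assumptions: the Visit 8 window, the spread of Visit 9, the day of the last dose, and the decay of HbA1c. With a +/-7 day Visit 8 window, the realistic spread of Visit 9 costs a few tenths of a percentage point of power, and the extreme case costs about 2 to 4 points. A +/-3 day window costs nothing. The probable direction is slight dilution. The sample size is not in question. The correction is worth making before unblinding because it concerns the primary value and is cheap.

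**What to change.** Add to SAP 6.7:

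> If a Visit 8 (EOT) HbA1c value falls in the Week 52 window (Day 310 or later), it is the Week 52 value. A Visit 9 (EOS) value is used for Week 52 only if no Visit 8 value is available and it lies within stop date + 7. An EOS value does not replace an available EOT value for LOCF. Rescue censoring is applied before selection.

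The condition on Day 310 matters. Without it, the sentence would conflict with note A of Table 6.7: 2, which assigns an early-discontinuation Visit 8 to the earlier window it falls in, so that the window "will end X days after the trial medication stop date, including Day X". Note A and the 7-day allowance stay as they are. Visit 9 should not be barred altogether, because it is a usable fallback when the Visit 8 sample is missing.

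The two timings of Visit 9, from EOT in Protocol 3.1 and from the last dose in Protocol 6.2.3, must be reconciled, since they decide whether the sample falls inside the window.

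The cost is one programming condition, and a selected value that is sometimes a few days further from Day 365. With the rule in place no Visit 9 value is selected over an available Visit 8 value, and the sample size is unchanged.

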7. PLANNED ANALYSIS

Disposition of the patient population participating in the trial will be analysed by treatment groups and presented in the clinical trial report as a frequency-distribution.

A frequency of patients with iPDs, also summarised by whether the iPD led to exclusion from the PPS, will be presented by treatment group for the RS. The frequency of patients in different analysis sets will also be analysed for each treatment group.

For in-text tables presenting descriptive analysis of the endpoints and other variables (analysed in original scale), the set of summary statistics is: N (number of patients with nonmissing values), mean, SD.

For end-of-text tables, the set of summary statistics is: N (number of patients with nonmissing values) / Mean / SD / Min / Q1) / Median / Q3 / Max.

Statistical parameters will be displayed to a defined number of decimal places as specified in the BI guideline “Standards for Reporting of Clinical Trials and Project Summaries” (6).

Tabulations of frequencies for categorical data will include all possible categories and will display the number of observations in a category as well as the percentage (%) relative to the respective treatment group. Percentages will be rounded to one decimal place. The category missing will be displayed if and only if there are actually missing values. Percentages will be based on all patients in the respective patient set whether they have non-missing values or not.

In all specified statistical analyses, treatment comparisons will be made between randomised empagliflozin group and placebo.

Descriptive statistics on the impact of COVID-19 on study visits as well as trial medication intake will be provided if any.

7.1 DEMOGRAPHIC AND OTHER BASELINE CHARACTERISTICS

Descriptive analysis of the following demographic variables measured at baseline will be presented:

Sex, age (in years), age groups, BMI (kg/m²), BMI categories, history of hypertension(Yes / No), height (cm), duration of diabetes (categories based on years), renal impairment (eGFR using MDRD formula), HbA1c (%) and HbA1c categories. Categories for baseline characteristics are defined in [Section 6.4](#).

Demographic and baseline characteristics tables will be presented for the FAS. A summary of the number of patients in each randomisation strata per treatment will also be shown. This will be based upon the data received from the IRT provider.

7.2 CONCOMITANT DISEASES AND MEDICATION

Only descriptive statistics are planned for this section of the report using the FAS. Concomitant medication use will be summarised by WHO ATC level 3 (ATC3) and preferred name. Summaries will be presented for concomitant therapies taken during randomised

treatment, taken at baseline and those newly introduced during randomised treatment. Separate summaries of use of acetylsalicylic acid (ASA), antihypertensives or lipid lowering drugs at baseline by preferred name will be presented. The following codes from the SDGs will be used to define ASA, antihypertensives and lipid lowering drugs:

- ASA: 50000019
- Antihypertensives: 000000049
 - Adrenergic receptor agonists: 000000051
 - Adrenergic receptor antagonists: 000000050
 - Angiotensin converting enzyme (ACE) inhibitors: 000000053
 - Angiotensin II receptor antagonists: 000000054
 - Calcium channel blockers: 0000000769
 - Renin inhibitors: 000000095
 - Other antihypertensives: 000000055
- Lipid lowering drugs: 600000014
 - Niacin: 600000008
 - Fibrates: 600000009
 - Statins: 000000096
 - Ezetimibe: 50000014
 - PCSK9: 50000011
- Other lipid lowering drugs: 600000010

Concomitant diseases will be summarised by MedDRA SOC and PT. Relevant medical history by treatment group will also be presented. Both summaries will be presented using the FAS.

7.3 TREATMENT COMPLIANCE

Only descriptive statistics are planned for this section of the report. The number and percentage of patients with overall compliance will be reported. The sum of all reported compliance over the planned visits (disregarding run-in) will be divided by the total duration (until last visit where medication is returned) to derive the overall compliance. The FAS will be considered.

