4.1.4 Drug assignment and administration of doses for each patient

Eligible patients will be randomised to empagliflozin 10 mg or placebo. Medication will be dispensed in a double-blind manner. The empagliflozin dosing is described in Table [4.1.4:1](#).

Patients will be assigned a placebo run-in kit at the beginning of the placebo run-in period (Visit 2), and this kit will contain sufficient medication for the run-in period within visit window. Dispensing of kits for the double-blind treatment period will begin at Visit 3 and occur on 5 occasions over a period of 52 weeks.

From the start of the placebo run-in period (Visit 2), patients should be instructed to take their trial medication, 1 tablet with water, once daily in the morning. To ensure a dose interval of about 24 hours, the medication should be taken at the same time each day. If a dose is missed by more than 12 hours, that dose should be skipped and the next dose should be taken as scheduled. No double doses should be taken, and dose reductions are not permitted. Empagliflozin can be taken with or without food.

Patients should be instructed not to take their trial medication on the morning of study visits as they will be dosed while patient is in the trial site. Patients who fail to do so should have the visit rescheduled as soon as possible, ideally on the following day. Visits should be routinely scheduled in the morning, at approximately the same time of day for each visit. The

actual date and time of administration of the medication at the trial visit will be recorded in the eCRF.

Patients will continue with their standard of care throughout the entire study.

Table 4.1.4: 1 Empagliflozin dose administration schedule

		Total units per dose	Timing
Placebo run-in period (open-label)			
All patients	matching placebo	1 tablet	once daily, morning
Randomised treatment period (double-blind)			
10 mg	active drug	1 tablet	once daily, morning
or			
Placebo	matching placebo	1 tablet	once daily, morning

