4.1.6 Packaging, labelling, and re-supply

The investigational medicinal products will be provided by BI or a designated contract research organisation (CRO). They will be packaged and labelled in accordance with the principles of Good Manufacturing Practice (GMP). Re-supply to the sites will be managed via an IRT system, which will also monitor expiry dates of supplies available at the sites.

For details of packaging and the description of the label, refer to the ISF.

The study medication will consist of packs labelled with the trial identification and medication kit number. Each pack will contain an appropriate number of empagliflozin tablets or placebo to empagliflozin with some reserve (see below) for dosing until the next scheduled visit.

The kit for placebo run-in period, assigned to all patients successfully completing Visit 2, will contain 21 tablets (i.e., sufficient supply for 2 weeks, with 1 week in reserve). Each kit for double-blind treatment period will contain 35 tablets (i.e., sufficient supply for 4 weeks, with 1 week in reserve).

At Visit 3, the patient will receive 1 kit for double-blind treatment period. The patient will receive 2 kits at Visit 4, 3 kits at Visit 5 and 6, and 4 kits at Visit 7.

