4.3 TREATMENT COMPLIANCE

Patients are requested to bring all remaining trial medication including empty package material with them when attending visits.

Based on tablet counts, treatment compliance will be calculated as shown in the formula below. Compliance will be verified by the CRA authorised by the sponsor.

$$\text{Treatment compliance (\%)} = \frac{\text{Number of tablet actually taken} \times 100}{\text{Number of tablet which should have been taken as directed by the investigator}}$$

Proprietary confidential information © 2020 Boehringer Ingelheim International GmbH or one or more of its affiliated companies

If the compliance is smaller than 80% or larger than 120%, site staff will explain a reason in eCRF and remind to the patient the importance of treatment compliance.

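### SAP 7.3 derives overall compliance by dividing summed visit percentages by a duration, which does not give a compliance percentage

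*SAP*

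**What the plan says.** Protocol 4.3 sets the visit-level measure: "Based on tablet counts, treatment compliance will be calculated as shown in the formula below". The formula is tablets actually taken × 100, divided by tablets that should have been taken, so each visit's value is a percentage. The same section sets limits for site follow-up: "If the compliance is smaller than 80% or larger than 120%, site staff will explain a reason in eCRF".

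SAP 7.3 turns the visit values into one value per patient: "The sum of all reported compliance over the planned visits (disregarding run-in) will be divided by the total duration". The duration runs "until last visit where medication is returned) to derive the overall compliance". The output is a count: "The number and percentage of patients with overall compliance will be reported". The summary is descriptive and uses the FAS.

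SAP 7.3 does not give the unit of duration, any weighting of visits by interval length, or the range that makes a patient compliant. No text is redacted in that section.

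**The concern.** Adding percentages and dividing by a length of time gives percent per day or percent per week. For the result to be a percentage, either the divisor must be the number of visits, or each visit's value must first be multiplied by its interval. SAP 7.3 does neither.

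Two consequences follow if the rule is programmed as written. First, the score falls as follow-up lengthens even when adherence is constant, because later intervals are longer and each adds only one percentage to the sum. Early stoppers then look better than completers. Second, a poor result over 4 weeks counts as much as a poor result over 16 weeks.

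At stake is the reported number and percentage of compliant patients. That count also lacks a threshold, so it would stay undefined even with a working formula.

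**Working it through.** The documents state no compliance figure to reproduce, so the check applies the rule to patients whose true compliance is known. The visit-level values below are illustrative.

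**Inputs**

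- Visit compliance C_i, in percent: protocol 4.3.
- Dose: one tablet once daily (protocol 4.1.4), so tablets due equal days.
- Number of intervals: five dispensing occasions over 52 weeks (protocol 4.1.4).
- Interval lengths: protocol 4.1.6 gives one kit at Visit 3, and then "The patient will receive 2 kits at Visit 4, 3 kits at Visit 5 and 6, and 4 kits at Visit 7". Each kit is a 4-week supply plus reserve, so the intervals are 4, 8, 12, 12 and 16 weeks. The planned days in SAP Table 6.7: 2 (1, 29, 85, 169, 253, 365) agree: 28 + 56 + 84 + 84 + 112 = 364 days.

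**Formulas**

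- SAP rule as written: sum(C_i) / T, with T the duration to the last return.
- Interval-weighted compliance: sum(C_i × days_i) / sum(days_i). At one tablet daily this equals 100 × tablets taken / tablets due.

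**Step 1. Perfect compliance, last return at a scheduled visit**

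| Last return | Sum of C_i | SAP rule, days | SAP rule, weeks | True value |
|---|---|---|---|---|
| Week 4 | 100 | 100/28 = 3.57 | 100/4 = 25.0 | 100% |
| Week 12 | 200 | 200/84 = 2.38 | 200/12 = 16.7 | 100% |
| Week 24 | 300 | 300/168 = 1.79 | 300/24 = 12.5 | 100% |
| Week 36 | 400 | 400/252 = 1.59 | 400/36 = 11.1 | 100% |
| Week 52 | 500 | 500/364 = 1.37 | 500/52 = 9.62 | 100% |

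No row gives 100 in either unit. Against the protocol's 80% and 120% limits, every one of these patients would fall below 80.

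**Step 2. How far the ordering goes.** A patient whose last return is at Week 12, with the same compliance c at both visits, scores 2c/84 in days. This equals the perfect completer's score when c = (500/364) × 84/2 = 57.7%. Anyone in that position above 57.7% per visit scores higher than a perfect completer. Below it, the order reverses.

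**Step 3. Missing interval weights.** Take two completers, each with one visit at 50% and four at 100%.

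- 50% in the first 4 weeks: SAP rule 450/364 = 1.24; weighted (50 × 28 + 100 × 336)/364 = 96.2%.
- 50% in the last 16 weeks: SAP rule 450/364 = 1.24; weighted (100 × 252 + 50 × 112)/364 = 84.6%.

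The SAP rule gives both the same score, whatever the unit.

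**Step 4. Would averaging over visits repair it?** This divides by 5 instead of by duration, so it is a different rule, and it can move a patient across the protocol's 80% limit in either direction.

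- Visits at 100, 100, 100, 100, 30: mean 430/5 = 86.0%; weighted (100 × 252 + 30 × 112)/364 = 78.5%.
- Visits at 30, 100, 100, 100, 60: mean 390/5 = 78.0%; weighted (30 × 28 + 100 × 224 + 60 × 112)/364 = 82.3%.

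**Step 5. Tablets reading.** If the quantity summed were tablets taken, the rule in days would give 364/364 = 100% for a perfect completer and 84/84 = 100% for a perfect Week 12 stopper.

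**The case against.** The strongest reply is that the sentence is loosely worded but the intent is sound. With one tablet daily, tablets due equal days of treatment. Summing tablets taken and dividing by days to the last return gives exactly the protocol 4.3 quantity, and ending at the last return fits a tablet count. SAP 6.6.4 also converts tablets to treatment duration at one tablet per day, and SAP 7.7 reports each patient's exposure in days, so days is the natural unit. Scores such as 1.37 for perfect adherence would be noticed at the first output. The 96.2% and 84.6% patients both lie within 80% to 120%, so that pair would not change the count. Those limits are the only ones in the documents, and the SAP assumes familiarity with the protocol.

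Much of this stands. The tablets reading gives the right answer and may well be what was intended, days is the likeliest unit, and a literal implementation would probably be caught. It does not rescue the text, however. SAP 7.3 sums compliance, which the protocol defines as a percentage, and settling on days still yields percent per day. The SAP 6.6.4 provision concerns imputing a missing stop date and does not define compliance. A programmer who notices the problem could repair it by visit averaging or by interval weighting, and Step 4 shows that these can classify a patient differently, although the examples need a visit as low as 30%. The protocol's 80% and 120% limits trigger a site explanation and a reminder to the patient; neither document calls them an analysis cut-off.

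**Conclusion.** The rule is wrong as written. Taken with the protocol's definition of compliance, it returns 1.37 (days) or 9.62 (weeks) for a perfect completer instead of 100%. At equal per-visit compliance the score falls as follow-up lengthens, and the 4-, 8-, 12-, 12- and 16-week intervals count equally. This rests on reading reported compliance as the protocol 4.3 percentage and on returns at the scheduled visits. If tablets taken was meant, the formula is right and the wording needs correcting. The missing cut-off is a separate gap that remains under either reading.

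The point is minor. It concerns a descriptive FAS table, and neither the primary MMRM nor any other visible efficacy analysis uses it. Whether compliance can lead to exclusion from the PPS cannot be judged, because the important protocol deviations are defined in the DV domain (SAP sections 4 and 6.2), outside these documents.

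**What to change.** Replace the derivation in SAP 7.3 with: overall compliance (%) = 100 × total tablets taken / total tablets due, from the first double-blind dose to the last visit with returned medication. An equivalent form is the mean of the visit percentages weighted by interval days. Add the cut-off that defines a compliant patient for the reported number and percentage; the protocol's 80% and 120% limits are one option.

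The cost is one or two sentences in the SAP. It needs no new data, since the tablet counts are already collected for protocol 4.3.
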